Justification

It is necessary to have information about the prognosis of subjects with severe obesity and schizophrenia who undergo bariatric surgery. This knowledge will make it possible to establish clear guidelines for action in these cases.

Research questions

What is the long-term outcome after bariatric surgery in subjects with schizophrenia?

Hypothesis

Bariatric surgery in subjects with schizophrenia leads to an improvement in weight and cardiometabolic comorbidities similar to that of subjects without schizophrenia

3. GOALS:

Main goal:

To study the short (first year after bariatric surgery) and long-term (up to 5 years of follow-up after bariatric surgery) evolution in terms of weight loss of patients with obesity and schizophrenia who underwent bariatric surgery in Spain and compare it with the evolution of patients without psychiatric disorder.

Secondary objectives:

- Determine the casuistry of patients, with special interest in the characteristics of the underlying psychiatric pathology (years of evolution, clinical stability criteria, pharmacological treatment...).
- To Analyze the evolution of obesity comorbidities.
- To Analyze the evolution of psychiatric pathology after bariatric surgery: (decompensation, drug treatment...)
- To analyze the frequency of early (<30 days post-surgery) or late (>30 days post-surgery) post-surgical complications.

4. METHODS:

Study design

Retrospective case-control study.

Study population. Inclusion, exclusion criteria

Cases:

Inclusion) Both criteria must be met:

- 1.- Patients with severe obesity undergoing bariatric surgery and with follow-up in Spanish territory.
- 2.- Patient with schizophrenia or schizoaffective disorder.

Exclusion)

Subjects who do not meet any of the two inclusion criteria

Controls: in a 4:1 ratio with cases

Inclusion) Both criteria must be met:

- 1.- Patients with severe obesity undergoing bariatric surgery and with follow-up in Spanish territory.
- 2.- Absence of psychiatric pathology
- 3.- Paired with the cases by age, sex, BMI before surgery and type of surgery.

Exclusion)

Subjects who do not meet any of the two inclusion criteria

Definition of variables

Main variables:

- weight
- size
- BMI

- TWL (total weight loss)
- EWL (excess weight loss)

Secondary variables:

- Age, ethnicity, educational level
- Type of surgery
- psychiatric dx
- Years of evolution of the psychiatric disorder at the time of IQ
- Psychiatric drug treatment, lithium, medication load.

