- Number of psychiatric admissions prior to IQ.
- Number of psychiatric admissions/psychiatric emergencies after surgery (relapses): In-hospital relapses, Relapses < 30d, relapses during follow-up.
- Criteria for approval of surgery (in each center).
- Biochemical parameters: glucose, HbA1c, total cholesterol, triglycerides, HDL, LDL.
- Early and late postoperative complications and death of the patient.
- Presence of diabetes, arterial hypertension, dyslipidemia, OSAS and liver disease and treatments for these pathologies.
- Adherence to follow-up in endocrinology and dietetics (Number of visits attended/Number of scheduled visits)
- Lost to follow-up.

The collection of variables will be carried out pre-surgery and 1 month, 6 months, 12 months and subsequently annually until a maximum of 5 years of follow-up.

Expected sample size

All cases detected in Spanish territory

The minimum number of cases expected will be 10 patients based on the low casuistry of the problem. The number of patients in the control group will be x4 that in the study group.

Methodology. Information sources

The study population will be identified in each center in the usual specialty consultations or by searching the databases of each center. Review of medical records in search of the specified variables (retrospective observational study).

Data Management and Analysis

The coordinating researcher (Dra [name]) will be responsible for the creation of the database and its exploitation. The database will be created in Excell format and the SPSS program will be used for statistical analysis. The statistics will be mainly descriptive. For cases in which it is decided to compare groups, normality tests will be used to establish the behavior of the variables and parametric/non-parametric tests will be used as appropriate.

Data collection

The researcher will guarantee the accuracy and integrity of the data, as well as all the reports that are required. The data included in the Data Collection Notebook (CRD), which are derived from source documents, will be consistent with those documents or otherwise the discrepancies will be justified.

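### With no data cut-off or minimum time since surgery, and controls not matched on possible follow-up, the 5-year course and comparison partly reflect who was operated on earlier

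*Protocol*

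**What the plan says.** - **Horizon.** Protocol section 3 (Main goal) covers the first year and "long-term (up to 5 years of follow-up after bariatric surgery) evolution in terms of weight loss", and asks for a comparison with patients who have no psychiatric disorder.
- **Eligibility.** Section 4 (Study population) uses the same surgical criterion for cases and controls: "Patients with severe obesity undergoing bariatric surgery and with follow-up in Spanish territory". It names a place of follow-up but no length, surgery window or cut-off date.
- **Who enters.** Section 4 (Expected sample size): "All cases detected in Spanish territory". It adds: "The minimum number of cases expected will be 10 patients based on the low casuistry of the problem", and "The number of patients in the control group will be x4 that in the study group".
- **Matching.** Section 4 lists age, sex, preoperative BMI and surgical procedure. Neither date of surgery nor available follow-up is listed.
- **Schedule.** Section 4 (Definition of variables) sets collection before surgery, at 1, 6 and 12 months, and "subsequently annually until a maximum of 5 years of follow-up". This is a ceiling with no floor.
- **Loss.** The same list has the item "Lost to follow-up" without a definition, and an adherence ratio of attended to scheduled visits.
- **Time frame.** Section 5 (Work plan) puts patient identification and data entry in months 4 to 8 of a 12-month project.

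**The concern.** A patient operated on 18 months before extraction is eligible but cannot supply a value at years 2 to 5, and the project is too short for later visits to fall due. Two consequences follow.

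First, the set of patients behind each annual summary shrinks towards earlier operations. If patients from earlier years differ from recent ones in their weight loss, the curve from year 1 to year 5 adds that difference to the true change within patients, and loss followed by regain is what the long-term part of the goal is meant to show.

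Second, the matched sets need not hold together over time. A case due at year 5 may have controls who are not, and controls due at year 5 may belong to a case who is not. The year-5 comparison then loses the balance that matching was meant to give. An analysis plan can restrict who is compared, but it cannot supply controls with enough possible follow-up once the controls have been chosen.

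**Working it through.** **The plan's own figure.** There is no power calculation to reproduce. The only arithmetic is 4 × 10 = 40 controls at the minimum of 10 cases, 50 patients in all.

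**Assumption for sizing.** The Protocol gives no surgery dates. Assume that time since surgery at extraction is uniform on 0 to T years, with T from 6 to 15. Then:

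- cases due at year t = 10 × (1 − t/T);
- if a control's surgery date is unrelated to its case's, the expected number of its four controls due at year 5 = 4 × (1 − 5/T).

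| T (years) | Cases due, year 1 | Cases due, year 5 | Year 5 as share of year 1 | Controls due at year 5, of 4 |
|---|---|---|---|---|
| 6 | 8.3 | 1.7 | 20% | 0.7 |
| 8 | 8.8 | 3.8 | 43% | 1.5 |
| 10 | 9.0 | 5.0 | 56% | 2.0 |
| 15 | 9.3 | 6.7 | 71% | 2.7 |

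This is before any true loss.

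**Matched sets at T = 10.** Of 40 controls, 40 × 0.5 = 20 are due at year 5. The 5 cases due have 5 × 4 = 20 controls, of whom 20 × 0.5 = 10 are due. The other 10 controls due belong to cases with no year-5 value. An unmatched comparison of 5 cases with 20 controls would thus draw half its controls from sets whose case is absent.

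**Precision.** The 95% half-width of a case-control difference in SD units, ignoring the matching, is 1.96 × √(1/n + 1/(4n)). It is 0.69 with 10 cases, 0.98 with 5 and 1.10 with 4. With 5 cases and only their 10 due controls it is 1.96 × √(1/5 + 1/10) = 1.07.

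**How composition enters the course.** Suppose half the cases are early operations with year-1 loss E, half are recent with loss R, all have reached year 1, and everyone regains g points by year 5. The change between visit means is (E − g) − (E + R)/2 = (E − R)/2 − g. With the invented values E = 35%, R = 27% and g = 3, the year-1 mean is (5 × 35 + 5 × 27)/10 = 31% and the year-5 mean is 35 − 3 = 32%: an apparent gain of 1 point where every patient regained 3. The sign reverses only if E − R exceeds 2g, here 6 points. Smaller differences bias the size of the regain but not its sign.

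**Loss to follow-up.** At T = 10 with an assumed true loss of 20% among those due, 5 cases are not yet due, 5 × 0.2 = 1 is lost and 4 are observed. Over all cases, 6/10 = 60% lack a year-5 value; among those due the figure is 1/5 = 20%.

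**The case against.** Much can be said for the plan as written.

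- **Variable follow-up is stated openly.** Both the goal and the schedule give five years as an upper limit. Taking every available case is reasonable when as few as 10 are expected. This stands, and the fix leaves case entry alone.
- **Analysis sets and the definition of loss usually belong in an analysis plan.** This stands for the undefined loss item, which alone would be missing detail and no finding. It does not cover the choice of controls, which the Protocol itself fixes by its matching factors.
- **The Protocol does not say that each visit will be summarised on whoever has a value.** Correct: it says only that the statistics are mainly descriptive, with tests where groups are compared. The risk is one the stated rules leave open; it is not a declared method.

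Some stronger readings are tempting but unsupported. A reader might infer that years 1 and 5 describe different patients; in fact the later group is a subset of the earlier one. Nor does year 1 include everyone, since nothing requires even one year since surgery. A reader might also infer that a lost patient cannot be told from one not yet due. But visits timed from surgery, complications split at 30 days and the attended-to-scheduled ratio all imply that the date of surgery is known from the records. Finally, the reversal of sign rests on an invented 8-point difference between early and recent operations, and any single figure such as 50% not due rests on one assumed spread of dates. Matching on procedure also closes one route by which surgical era could separate the groups.

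**Conclusion.** The point holds as a weakness of the matching and entry rules. They let the year-5 group be a selected subset of earlier operations and let a case's year-5 value stand without comparable controls, so the long-term part of the main goal can reflect when patients were operated on as well as how their weight changed.

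The size cannot be fixed from the document. Under uniform surgery dates over the past 6 to 15 years, about 2 to 7 of 10 cases would be due at year 5, against 8 to 9 at year 1. Whether this biases the course depends on whether weight loss differs by date of surgery, and the between-group effect depends on whether cases and controls differ in their dates. The Protocol informs neither. It does not show that any result will have the wrong sign or that loss to follow-up will be overstated; it omits the rules that would prevent both.

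**What to change.** Keep all cases, and:

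1. State a data cut-off date and list the date of surgery among the variables collected.
2. Add to the control criteria that the control's surgery must allow at least the same possible follow-up as its case, up to the five-year ceiling. Judge this from the date of surgery and the cut-off, not from whether a late weight was recorded; otherwise controls would be selected for staying in follow-up.
3. At each visit, compare only matched sets whose case was due for that visit, and report the numbers due and observed.
4. Show the 1-to-5-year course also in the fixed group due for year 5.
5. Count loss to follow-up only among patients whose visit was already due.

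The cost is small: a stated date, one data field, one extra matching criterion and a reporting rule. The extra constraint makes 4:1 matching somewhat harder, and controls of cases not yet due drop out of the late-visit comparison. No case loses a year-5 value, because a case under five years from surgery has none.

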Principal investigators and participating centers	[name] Psychiatry Hospital of Santa Creu i Sant Pau [name]: Hospital del Mar. Barcelona [name] : Reina Sofia University Hospital. Cordova [name] : Parc Taulí University Hospital [name] : A Coruña University Hospital [name]: Gregorio Marañoñ University Hospital, Madrid [name]: University of Navarra Clinic. Pamplona [name] : Hospital Clínic, Barcelona [name]: León University Assistance Complex [name]: Valle del Nalón Hospital. Asturias [name]: Vigo University Hospital Complex, Pontevedra [name]: Arnau de Vilanova University Hospital. Lleida [name]: San Carlos Clinical Hospital, Madrid [name]: Bellvitge University Hospital [name]: Hosp. Univ. Virgen del Rocio of Seville [name]: Regional University Hospital of Malaga

	
[name]: Germans Trias i Pujol University Hospital. badalona [name] : Virgen de la Macarena Hospital, Málaga [name] : Hospital Mutua de Terrassa, Terrassa. [name] : Son Llàtzer Hospital, Majorca [name]: Trueta Hospital, Girona [name] : University Hospital of the Canary Islands, Tenerife. [name] :H. Virgin of Light-Cuenca [name] : H. University Virgen de la Victoria-Málaga. [name] : Reina Sofia-Córdoba University Hospital [name] : Viladecans Hospital, Barcelona [name] : H. University [name]: [name] : H. San Carlos Clinic in Madrid [name] : H. de Reus [name] : H. General of Vic

Reference ethics committee	CEIM of the Hospital de la Santa Creu i Sant Pau
Main goal	To study the evolution after bariatric surgery in patients with obesity and schizophrenia
Design	Multicenter retrospective case control study.
Disease under study	Schizophrenia and Obesity
Methodology	Retrospective observational study
Study population and total number of subjects	Cases: Patients with schizophrenia and obesity undergoing bariatric surgery. (number: all cases collected within the GOSEEN group). Controls: Patients without psychiatric pathology matched by age, sex, BMI and type of surgery and in a 4:1 ratio to cases.
Calendar. Expected duration of the study.	12 months

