ethical considerations	Informed consent will be obtained from patients who are currently being followed up at the reference centers.
Funding source	Not precise

2. THEORETICAL FRAMEWORK. PROBLEM STATEMENT:

Background

Obesity affects approximately 45-55% of patients with schizophrenia (1). Weight gain in these patients may be due to different factors such as the use of antipsychotic drugs with an unfavorable metabolic profile, the coexistence of sleep disorders or negative cognitive symptoms that often translate into a more sedentary lifestyle and alterations in eating behavior, among others (2). The coexistence of obesity and its comorbidities in this group of patients significantly worsens both their physical and mental health (3). In fact, cardiovascular disease is one of the main causes of mortality in patients with schizophrenia (4).

Lifestyle interventions, while they may be effective in people with schizophrenia (5), often fall short of achieving weight goals. At present, obesity surgery represents the most effective treatment in terms of weight loss and resolution of comorbidities, being indicated in cases of patients with a body mass index (BMI) > 35 kg/m² with comorbidities or BMI > 40 Kg/m² with/without comorbidities. However, the access of patients with schizophrenia to bariatric surgery techniques is usually limited by different factors such as fear of a possible worsening of the underlying disease, or a lower weight loss in this population, among others. In addition, clinical practice guidelines recommend that all patients with psychiatric pathologies be evaluated in a regulated manner prior to surgery (6), although the content of this evaluation and the criteria for declining or accepting surgery are not clear. Although the course of schizophrenia is variable and its symptoms may be stable without being a clear contraindication for bariatric surgery, in actual practice, a considerable number of professionals contraindicate bariatric surgery in the presence of a psychotic disorder (7).

For these reasons, data on the efficacy of bariatric surgery in patients with schizophrenia are scarce and limited to very small case series with short-term follow-up (2,8,9). Our objective is therefore to carry out a multicenter retrospective study that allows us to study the long-term evolution after bariatric surgery in a large series of patients, focusing not only on weight evolution but also on the long-term evolution of psychiatric pathology.

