It is the responsibility of the investigator to obtain the informed consent of the patient. The patient will not be able to participate in any study-specific procedure without obtaining their consent, or that of their legal guardian/family member when the patient is unable to give consent due to their clinical situation.

Before including any subject in the study and before obtaining informed consent, the investigator or the person designated by the investigator will explain to the potential participating subject or their legal guardian/family member the objectives, methods, and potential risks of the study and any inconvenience it may cause. The explanation about the nature, scope and possible consequences of the study will be made in an understandable language.

The prospective participant or their legal guardian/family member should have time to consider their decision to participate in the study, and have the opportunity to ask questions. After this explanation, and before entering the study, the consent must be properly recorded by the signature of the subject or their legal guardian/family member. Given the retrospective nature of the study, it is likely that some patients to be included have died or are no longer seen at their referral center. In this case, informed consent will not be obtained, but the research team undertakes to verify that there is no record of the subjects' express opposition in the clinical history and to comply with the confidentiality regulations.

In addition, since the use of pseudonymized personal data for biomedical research purposes requires technical and functional separation between the research team, and those who perform the pseudonymization and keep the information that enables re-identification, the person who performs the pseudonymization for this study does not will be part of the research team.

For access to the pseudonymous data, an express commitment of confidentiality and not to carry out any re-identification activity is sent, and that specific security measures will be adopted to avoid re-identification and access by unauthorized third parties.

The Model Patient Information Sheet and the Consent Form are presented as an Annex.

Considerations on the treatment of biological samples

Does not apply

Data confidentiality

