Annex 1: Study evaluations

Annex 2: Information sheet for subjects (presented in a separate document)

Annex 3: Informed consent form (presented in a separate document)

Appendix 1

STUDY EVALUATION SCHEME

Procedure \ Visit	V0	V1
Sign informed consent		x (in patients who are still being monitored at their center)
Inclusion/exclusion criteria	x	
Retrospective collection of variables	x	
Collection of anthropometric and sociodemographic variables	x	
Collection of laboratory variables	x	
Collection of post-surgical clinical evolution variables	x

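### Identifying patients in consultations alone complies with the protocol, although it counts on including patients who have died or no longer attend; require the database search in every centre for both groups

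*Protocol*

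**What the plan says.** **Identification.** Protocol section 4, *Methodology. Information sources*: "The study population will be identified in each center in the usual specialty consultations or by searching the databases of each center". The variables are then taken from the medical records. No section makes the database search compulsory, and none requires the same route in every centre or for cases and controls.

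**Who is wanted.** *Expected sample size* in section 4 gives "All cases detected in Spanish territory", with a minimum of 10 and four times as many controls. The synopsis gives "all cases collected within the GOSEEN group". Section 6, on informed consent, says "it is likely that some patients to be included have died or are no longer seen at their referral center" and allows these patients to be included without consent if no express opposition is on record. In line with that, the synopsis says "Informed consent will be obtained from patients who are currently being followed up at the reference centers", and the consent row of the Appendix 1 scheme has the same restriction. Inclusion criterion 1 (section 4) asks for follow-up in Spain, without saying whether past follow-up is enough.

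**What is measured.** The main goal is weight loss in the first year and up to 5 years, compared with patients without psychiatric disorder. Secondary variables include death, adherence to scheduled visits and loss to follow-up.

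**Controls.** "Controls: in a 4:1 ratio with cases"; "Paired with the cases by age, sex, BMI before surgery and type of surgery". Nothing says which four are taken when more qualify.

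**The concern.** A patient found because he or she still comes to clinic has, by that fact, survived and stayed in follow-up. Both are things the study sets out to describe, and both may be related to weight course. The protocol clearly means to include patients who no longer attend, but it does not require the one listed route that can be relied on to find them.

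Two things are at stake. The first is the description: among patients found only in current consultations, recorded death and loss to follow-up will be too low and adherence may look too good. The second is the comparison: the text would allow cases to be found by a database search and controls in clinic, or the reverse, and would allow centres to differ. The contrast would then mix the effect of schizophrenia with the effect of how patients were found. The hypothesis is one of similar improvement, so a shift in either direction could mislead. No later analysis can restore patients who were never identified.

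A lesser matter concerns the controls. Their weights after surgery are already on file when the four are chosen, and nothing stated keeps that choice independent of those weights.

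**Working it through.** **1. The statements side by side.**

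| Place in Protocol | What it implies |
|---|---|
| Section 4, information sources | Either route alone complies |
| Synopsis; section 4, expected sample size | All cases found are wanted |
| Section 6, informed consent | Some included patients will be dead or no longer seen |
| Synopsis, ethics row; Appendix 1 | Consent only from those still followed, so others are in the study too |
| Section 4, variables | Death, adherence and loss to follow-up are recorded |

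The last four rows need a source that does not depend on attendance. The first row does not secure one. A clinician may remember a patient who died or left, but that is not a search.

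**2. When the comparison is affected.** Let m be the share of a group no longer attending, and d the difference in mean outcome (in SD) between attenders and non-attenders. The whole-group mean is (1 − m) × attender mean + m × non-attender mean. A sample of attenders alone is therefore off by m × d. The bias in the case–control contrast is m(cases) × d(cases) − m(controls) × d(controls).

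The documents give neither m nor d. Taking d equal in both groups, with assumed values:

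| Missed, cases / controls | d = 0.3 | d = 0.5 | d = 0.8 |
|---|---|---|---|
| 30% / 30% | 0 | 0 | 0 |
| 50% / 30% | 0.06 | 0.10 | 0.16 |
| 50% / 10% | 0.12 | 0.20 | 0.32 |

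The sign is open. If cases come from databases and controls from clinics, m(cases) is 0 and the sign reverses for the same d.

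**3. Scale.** The protocol's minimum is 10 cases, hence 4 × 10 = 40 controls. With equal variances and independent outcomes, the SE of the difference is √(1/10 + 1/40) = 0.354 SD. The last table row is then 0.12/0.354 = 0.3 to 0.32/0.354 = 0.9 SE.

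**4. Descriptive rates.** These are affected even in the 30%/30% row. If 30% of each group has died or left and only attenders are found, that 30% is absent from the record in both groups, although the contrast in weight is unchanged.

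**5. Choice of four controls (secondary).** Suppose n candidates qualify per case and the four highest are taken on some feature, such as completeness of records, that correlates ρ with a normally distributed outcome. The control mean then shifts by ρ × the mean of the top four normal order statistics, which is 0.725 for n = 8 and 1.019 for n = 12.

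| ρ | n = 8 | n = 12 |
|---|---|---|
| 0 | 0 | 0 |
| 0.1 | 0.07 SD | 0.10 SD |
| 0.3 | 0.22 SD | 0.31 SD |

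At ρ = 0.3 that is 0.22/0.354 = 0.6 to 0.31/0.354 = 0.9 SE. Both ρ and n are assumed. These figures show what an open rule could allow; they are not evidence of bias in this study.

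**The case against.** The best reply is that 'or' simply lists two sources to be used as available. The rest of the protocol points towards reaching non-attenders, and no section says that any centre will rely on clinics alone. That is fair as far as it goes: the database route is allowed, and clinic-only identification is permitted, not prescribed. But a centre that reads the sentence literally is within the protocol, and the consequence falls on variables the study reports.

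A reader might go further and infer that the protocol promises a complete census and then breaks the promise. It does not: it speaks of cases detected, or collected within the group, which is softer.

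A reader might also infer that controls will be chosen by outcome, or that leaving centre and surgery date out of the pairing is a mistake. Neither is supported. No section ties the choice to outcome, the four stated pairing factors are a legitimate set, and imbalance in centre or date can be adjusted for in the analysis. Details of the matching procedure may also sit in an analysis plan that is not shown. The control part therefore stands only as an optional improvement.

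Finally, none of the shifts above comes from this trial. That stands in full.

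**Conclusion.** The point holds in limited form. The identification sentence permits a route that selects on continued attendance, which fits badly with the protocol's own expectation of including patients who have died or left and with its reporting of death, adherence and loss to follow-up. The comparison over up to 5 years can be biased if the route differs between centres or groups. It is not biased if the route acts alike in cases and controls, meaning that the share missed times the difference is the same in both. The descriptive rates are affected in either event. Direction and size cannot be derived from the documents; the 0 to 0.32 SD range rests wholly on assumed shares and differences. To say that the study's results will be biased would go beyond the text.

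The wording should be changed before patients are identified, because the analysis cannot make up for it afterwards. Confidence is medium.

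**What to change.** **Main change, section 4, information sources:** *In every centre, all cases and all candidate controls are identified by searching the centre's databases, whether or not they still attend; usual consultations are only a supplement.*

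**Section 4, inclusion criterion 1, both groups:** word the requirement of follow-up in Spain so that past follow-up suffices, in line with section 6.

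**Optional, control criterion 3, add:** *Among candidates who meet the pairing criteria, with tolerances for age and BMI set beforehand, controls are chosen by a rule fixed in advance that uses pre-surgery data only: same centre where possible, then nearest surgery date, ties broken at random.* Keep centre and surgery date in the analysis file so that remaining imbalance can be adjusted for.

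**Cost:** one database query per centre, by a route the protocol already allows and for patients whose inclusion section 6 already covers, plus a little work in selecting controls. The ranking only orders candidates who already qualify, so in itself it neither loosens the pairing nor reduces the number of controls. One limit remains: the search finds patients who stopped attending, but it cannot supply weights that were never recorded.

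### The 5-year weight comparison rests on simple tests of available weights, so outcome-related loss that differs between cases and controls could bias it in either direction

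*Protocol*

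**What the plan says.** - **Aim** (Protocol, section 3, Main goal): compare short-term and "long-term (up to 5 years of follow-up after bariatric surgery) evolution in terms of weight loss" with patients without a psychiatric disorder.
- **Hypothesis** (section 2): surgery in schizophrenia "leads to an improvement in weight and cardiometabolic comorbidities similar to that of subjects without schizophrenia".
- **Schedule** (section 4, Definition of variables): data are collected "pre-surgery and 1 month, 6 months, 12 months and subsequently annually until a maximum of 5 years of follow-up". That is 3 visits in year 1 and 4 annual visits after it, so up to seven post-surgery weights per patient.
- **Loss**: "Lost to follow-up" is listed as a secondary variable, as is the ratio of attended to scheduled visits. No expected rate is given for either group.
- **Analysis** (section 4, Data Management and Analysis): the work is to be chiefly descriptive, and comparing the groups is left optional. Where a comparison is made, the method is that "normality tests will be used to establish the behavior of the variables and parametric/non-parametric tests will be used as appropriate". SPSS is the named software. No other inferential method appears.
- **Limitations** (section 4): only the retrospective nature is named.

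**The concern.** A normality check that chooses between a parametric and a non-parametric test is the ordinary description of a two-group comparison of one variable at one time. Such a test can use only patients with a weight at that time. For a patient last weighed at year 2, it drops the weights already recorded at 1, 6, 12 and 24 months. Those weights are the evidence on whether the lost patients were doing better or worse than those who stayed.

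The hypothesis is one of similarity. A distortion of the 5-year difference could therefore hide a real deficit in cases, or it could create or enlarge one. The protocol intends the result to inform guidance on offering surgery to these patients. It records the data needed to deal with the problem but does not connect them to the main comparison.

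**Working it through.** **Inputs from the protocol.** Minimum 10 cases; four controls per case, so 10 x 4 = 40 controls; up to seven post-surgery weights. It states no loss rate, SD, effect size or margin, so there is no figure of its own to reproduce. Everything below rests on assumed inputs. Differences are cases minus controls, and positive values favour cases.

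**Step 1: direction, by formula.** Let *d* be the share lost and rho the correlation between weight loss and staying in follow-up. The mean of those who remain shifts by rho x phi(z_d)/(1-d) SD, where z_d is the *d* quantile of the standard normal and phi its density.

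- *d* = 0.20: 0.280/0.80 = 0.350
- *d* = 0.40: 0.386/0.60 = 0.644
- *d* = 0.50: 0.399/0.50 = 0.798

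Take a true deficit in cases of -0.50 SD:

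| Lost, cases v controls | rho, cases / controls | Observed difference (SD) |
|---|---|---|
| 20% v 20% | 0.5 / 0.5 | -0.50 |
| 40% v 20% | 0.5 / 0.5 | -0.50 + 0.322 - 0.175 = -0.35 |
| 50% v 20% | 0.5 / 0.5 | -0.50 + 0.399 - 0.175 = -0.28 |
| 40% v 20% | -0.5 / -0.5 | -0.50 - 0.322 + 0.175 = -0.65 |
| 40% v 20% | 0 / 0.5 | -0.50 - 0.175 = -0.67 |

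Equal loss with equal dependence on outcome gives no bias in the difference. Unequal loss moves it either way.

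**Step 2: size in %TWL points, by simulation.** Assumed: mean %TWL falling from 30 at year 1 to 25 at year 5, SD 8.5, year-to-year correlation 0.85, no true difference. The yearly log-odds of loss rise by 0.5 or 1.0 per SD lower last observed %TWL. Bias in the 5-year difference among patients still attending:

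| Lost by year 5, cases v controls | Slope 0.5 | Slope 1.0 |
|---|---|---|
| 40% v 20% | +0.7 | +1.1 |
| 50% v 20% | +1.1 | +1.8 |
| 60% v 30% | +1.3 | +1.9 |
| Equal loss | about 0 | about 0 |
| 20% v 40% | about -0.7 | about -1.1 |

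These figures are approximate to 0.1 or 0.2. With a true deficit of 4 points and more cases lost, attenders show a deficit of only 2.1 to 3.3 points.

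**Step 3: does using the earlier weights help?** A two-visit simulation assumed a true 5-year deficit of 0.50 SD, a 12-month deficit of 0.30 SD, correlation 0.7 between the visits, and loss driven by the 12-month result.

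| Lost, cases v controls | Attenders only | Using earlier weights |
|---|---|---|
| 40% v 20% | -0.36 | -0.51 |
| 50% v 20% | -0.28 | -0.50 |
| 30% v 30% | -0.50 | -0.50 |

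The recovery follows from the assumption that loss depends only on recorded weights. It does not show what happens when loss depends on weights never recorded.

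**Step 4: compare with precision.** The 95% half-width at 10 v 40 is 1.96 x sqrt(1/10 + 1/40) = 0.69 SD, or 0.69 x 8.5 = 5.9 points. With 40% of cases and 20% of controls lost, 6 v 32 remain: 1.96 x sqrt(1/6 + 1/32) = 0.87 SD, or 7.4 points.

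**The case against.** **The protocol does not say this.** It never states that tests are run visit by visit or on attenders only. Comparisons are optional within a mainly descriptive analysis, and a parametric test could be a repeated-measures one. This stands as a limit on the wording: the visit-by-visit reading is the natural one, not a stated rule.

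**Missing-data rules belong in a statistical analysis plan.** One may exist and is not at hand, so the absence of such rules is no fault. What remains is that the one method the protocol does name fits poorly with its 5-year repeated-weight objective.

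**The bias favours the study's own hypothesis.** A reader might infer this, because loss of poorly responding cases would make the groups look alike. The documents do not support it as a conclusion. It needs more loss, or more outcome-related loss, among poorly responding cases, and no rates are given. The reverse pattern exaggerates a deficit.

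**The consent section proves that weights will be missing.** It says "it is likely that some patients to be included have died or are no longer seen at their referral center", which explains why consent may be unobtainable now. A patient who left after year 5 can have a complete record, so this is weak evidence. The recorded loss and adherence variables are better evidence that loss is a practical prospect.

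**The bias is small beside the imprecision.** At the minimum of 10 cases this is true: at most about 1.9 points against a half-width of 5.9 or more. But 10 is a floor for a study that seeks every case in Spain, and bias does not shrink as cases are added.

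**Conclusion.** The concern holds in a conditional form. The stated method, read in the usual way, leaves the 5-year difference open to bias when loss is related to weight loss and differs between groups. Under the assumed inputs the bias runs from about -1.1 to +1.9 %TWL points, through zero at equal loss. Neither its presence nor its direction can be settled from the documents, because they give no loss rates. A better method is available in the named software, with data the study already plans to collect. The change is worth making. It does not cure the poor precision at the minimum sample, where a non-significant result should not be read as evidence of similarity.

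**What to change.** In section 4, Data Management and Analysis:

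1. Name as the main comparison one linear mixed model (SPSS MIXED) for %TWL on all recorded post-surgery weights, with group, visit, group-by-visit and pre-surgery BMI.
2. Account for the 4:1 matched sets, for example with a matched-set random effect or by adjusting for the matching variables (age, sex, BMI, type of surgery).
3. Use a simple covariance structure, since there may be only 10 cases.
4. Report the 12-month and 5-year differences with 95% confidence intervals from this model.
5. Report loss to follow-up by group and visit.
6. Add one sensitivity analysis that assigns worse weight loss to lost patients.
7. Keep simple per-visit tests as description.

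The cost is a change of wording and a few hours of analysis, with no new data. The downside is small: the model assumes that loss is explained by the recorded weights, which is why item 6 is needed.
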